9.2.2 Intent to Treat Population

Anyone randomized and receiving at least one dose of study drug will be included in the intent to treat population.

9.2.3 Toxicity Evaluation

All participants will be evaluable for toxicity from the time of their first dose of study drug, Tofacitinib 5 mg, orally, twice daily.

9.3 STATISTICAL ANALYSES

9.3.1 General Approach

Demographics and clinical variables will be summarized by treatment group for each study visit. For continuous variables, descriptive statistics includes mean, standard deviation, median, and range. For categorical variables, counts and percentages will be reported. Due to exploratory nature of this study, statistical testing will be performed at the two-sided 5% level for the efficacy variables. The 95% confidence interval will be provided as well.

9.3.2 Analysis of the Primary Endpoints

The primary goal is to evaluate the safety and tolerance of Tofacitinib in participants with SS. For the safety population, the number and percentage of subjects with any AE, any related AE, any SAE, any Grade 3 and 4 toxicities not fulfilling the criteria for SAE, and non-serious adverse events and SS disease flares, as well as the total number of events for each category will be summarized by treatment group. AE's/SAE's will be reported from the time of consent. Events that are reported prior to the first treatment will be considered non-treatment emergent in analyses.

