1 PROTOCOL SUMMARY

1.1.1 SYNOPSIS

Title:	Safety of Tofacitinib, an oral Janus kinase (JAK) inhibitor, in primary Sjögren's syndrome (SS); a Phase Ib-IIa placebo controlled clinical trial and associated mechanistic studies
Study Description:	As a primary objective, this study represents an innovative investigative measure of the safety and tolerability of JAK inhibition in participants with primary Sjögren's syndrome. Secondary objectives will include investigating the effects of Tofacitinib on target tissues (e.g., salivary glands), systemic inflammation, and on vascular function in SS participants. We also aim to identify biomarkers of response that may be useful as endpoints in future studies.
Objectives:	
Primary Objective:
 
• To determine the safety and tolerability of Tofacitinib in participants with SS and mild to moderate disease activity. 
Secondary Objectives:
 
• To assess clinical improvement after treatment with Tofacitinib as measured by changes in the European League Against Rheumatism (EULAR) Sjögren's syndrome Disease Activity Index (ESSDAI) and no worsening on the Physician's Global assessment Scale (PGA).• To demonstrate that treatment with Tofacitinib is effective clinically and biologically in SS individuals with mild to moderate disease.• To investigate the effects of Tofacitinib on systemic biomarkers of SS as measures biological effects that can be used as outcome measures to power a larger Clinical Trial.
Endpoints:	
Primary Endpoint:
 
• Safety and tolerability will be measured by assessment of adverse events (AEs) and clinical safety laboratory tests throughout the study. Toxicity is defined as any study drug-related Grade 3 adverse event or higher (as measured by the National Cancer Institute (NCI), Common Terminology Criteria for Adverse Events (CTCAE), Version 5.0). 
Secondary Endpoints:
 
Preliminary assessments of clinical response will be measured by:
 
• Changes in the ESSDAI score between Baseline and Day 168 (end of treatment)

Abbreviated Title: Tofacitinib in Sjögren's syndrome

Version Date: 07/01/2024

- Changes in the Physician's Global Assessment (PGA) scores between baseline and study day 168.

Study Population:

Adult patients with Primary Sjögren's syndrome of mild to moderate disease activity

Phase:

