3 OBJECTIVES AND ENDPOINTS

OBJECTIVES	JUSTIFICATION FOR ENDPOINTS	ENDPOINTS
Primary		
To determine the safety and tolerability of Tofacitinib in participants with SS and mild to moderate disease activity.	This is an FDA approved drug that is not currently approved for use in the Sjögren's syndrome population. Tofacitinib has demonstrated both clinical and molecular potential to be an effective treatment for SS, however studies are lacking in this research population.	Safety and tolerability will be measured by assessment of adverse events (AEs) and clinical safety laboratory tests throughout the study. Toxicity is defined as any study drug-related Grade 3 or higher adverse event, as measured by the National Cancer Institute (NCI), Common Terminology Criteria for Adverse Events (CTCAE), Version 5.0).
Secondary		
To assess clinical improvement after treatment with Tofacitinib as measured by no change or improvement in the ESSDAI and no worsening on the physician's global PGA.	The ESSDAI was developed to be used as an outcome measure in clinical trials involving Sjögren's syndrome patient cohorts. It allows for assessment/scoring of major domain activity relevant to a SS population.	Assessments of clinical response will be measured by: 1) the change in ESSDAI between baseline and study day 168 2) No worsening of PGA between baseline and study day 168
To demonstrate that treatment with Tofacitinib is effective clinically and biologically in SS individuals with mild to moderate disease.	Data from a randomized placebo-controlled trial of Tofacitinib in SS would yield evidence to further pursue JAK/STAT pathway targeting in SS. Salivary flow rates are an objective measure of organ	Change in salivary flow rates between baseline and study day 168

OBJECTIVES	JUSTIFICATION FOR ENDPOINTS	ENDPOINTS
	function. Low salivary flow is a primary feature of SS and may be used as a non-invasive measure of therapeutic intervention.	

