8.6 ADVERSE EVENTS AND SERIOUS ADVERSE EVENTS

8.6.1 Definition of Adverse Event

Adverse events (AE) are any unfavorable and/or unintended diagnosis, symptom, sign (including an abnormal laboratory finding), syndrome, or disease that occurs during the study, having been either absent at baseline, or if present at baseline, appears to worsen.

Events will be reported as AE's as described in section 8.2.5.

All AEs will be graded for intensity (severity) according to CTCAE version 5.0 and relationship to study drug as described below.

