8.6.2 Definition of Serious Adverse Events (SAEs)

An adverse event (AE) or suspected adverse reaction is considered "serious" if, in the view of either the investigator, sponsor, or Pfizer, it results in any of the following outcomes:

- Results in death
- A life-threatening adverse event, (defined as a participant at immediate risk of death at the time of the event; it does not apply to an AE which hypothetically might have caused the death if it were more severe),
- Requires or prolongs hospitalization (i.e. the AE required at least a 24-hour inpatient hospitalization or prolonged a hospitalization beyond the expected length of stay; hospitalizations for elective medical/surgical procedures, scheduled treatments, or routine check-ups are not SAEs by this criterion),
- Results in a congenital anomaly or birth defect (i.e., an adverse outcome in a child or fetus of a Participant exposed to the trial drug prior to conception or during pregnancy),
- Causes a persistent or significant incapacity or substantial disruption of the ability to conduct normal life functions,
- Any other condition that, in the judgment of the investigator, represents a significant hazard or does not meet any of the above serious criteria but may jeopardize the participant and may require medical or surgical intervention to prevent one of the outcomes listed above
- Important medical events that may not result in death, be life-threatening, or require hospitalization may be considered serious when, based upon appropriate medical judgment, they may jeopardize the participant and may require medical or surgical intervention to prevent one of the outcomes listed in this definition. Examples of such medical events include allergic bronchospasm requiring intensive treatment in an emergency room or at home, blood dyscrasias or convulsions that do not result in inpatient hospitalization, or the development of drug dependency or drug abuse.

8.6.3 Medical Events Not Qualifying as Adverse Events or Serious Adverse Events:

Signs and symptoms of pre-existing medical conditions will not be recorded or reported as AEs or SAEs, unless they represent a clinically significant change from the baseline disease status documented at the Pre-screening Visit. In addition, hospitalization for elective procedures or surgeries will not be considered SAEs, nor will inpatient hospitalizations for convenience.

8.6.4 Clinical Laboratory Test Results Not Qualifying as Adverse Events or Serious Adverse Events:

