8.7.4 Time Period and Frequency for Event Assessment and Follow-Up

The occurrence of an adverse event (AE) or serious adverse event (SAE) may come to the attention of study personnel during study visits and interviews of a study participant presenting for medical care, or upon review by a study monitor.

All AEs including local and systemic reactions not meeting the criteria for SAEs will be captured on the appropriate case report form (CRF). Information to be collected includes event description, time of onset, clinician’s assessment of severity, relationship to study product (assessed only by those with the training and authority to make a diagnosis), and time of resolution/stabilization of the event. All AEs occurring while on study must be documented appropriately regardless of relationship. All AEs will be followed to adequate resolution.

Any medical condition that is present at the time that the participant is screened will be considered as baseline and not reported as an AE. However, if the study participant’s condition deteriorates at any time during the study, it will be recorded as an AE.

The severity of an AE will be documented at its highest level of severity. AEs characterized as intermittent require documentation of onset and duration of each episode.

Any time after informed consent is obtained, AEs and SAEs will be recorded and reported until 7 (for non-serious AEs) or 30 days (for SAEs) after the last day of study participation.

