9 STATISTICAL CONSIDERATIONS

9.1 STATISTICAL HYPOTHESIS

All analyses in this trial are descriptive and exploratory in nature. No formal statistical inferences are planned.

- Primary Endpoint(s): The primary objective is to evaluate the safety and tolerance of Tofacitinib in participants with SS. The primary endpoints include number and rates of adverse events (serious adverse events, Grade 3 and 4 toxicities not fulfilling the criteria for SAE, and non-serious adverse events) and number and rates of SS disease flares.
- Secondary Endpoint(s): Secondary endpoints will be analyzed by comparisons between the treatment (all SS participants receiving Tofacitinib) and placebo groups once the last participant completes the 28 weeks (196 days).
- Exploratory Endpoint(s):

For the following exploratory endpoints, all changes will be assessed between baseline and end of treatment, unless otherwise specified.

- Changes in salivary glands as assessed by histopathology including focus score, inflammation quantification and immunophenotyping of infiltrates
- Global transcriptomic changes in peripheral blood monocytes and minor salivary glands with specific interrogation of IFN regulated genes and other inflammatory pathways using software tools like Ingenuity Pathway Analysis.
- Differences between the treatment/placebo groups in changes in individual disease activity measures (ESSDAI, PGA, tear production, salivary flow) at the end of Study Day 168 will be analyzed as repeated measures with change from baseline as the dependent variable.
- Changes in participant reported outcomes such as: ESSPRI, SF-36, FSS, PROMIS
- Changes in non-invasive vascular studies
- A change will be analyzed using the appropriate statistical test per each type of data collected between baseline and at Day 168.

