10.7 SAFETY OVERSIGHT

In addition to the PI's responsibility for oversight, this study will be monitored by the NIDCR Division of Intramural Research Data and Safety Monitoring Committee (DSMC). The DSMC will include members with expertise in a broad range of areas, including, but not limited to, human subjects' protection, clinical trial implementation, biostatistics, rheumatology, and medical bone and mineral metabolism. The DSMC will meet periodically to assess safety and efficacy data (if applicable), study progress, and data integrity for the study. The DSMC will determine frequency of review at the first meeting, but typically will meet at least once a year. The DSMC may also choose to electronically review periodic data and safety reports in addition to convening data review meetings. If safety concerns arise, more frequent meetings may be held. In addition, unscheduled meetings can be requested by any party with responsibility of overseeing the study. The DSMC will provide recommendations to the NIDCR concerning the continuation, modification, or termination of the trial. The DSMC will operate under the rules of an NIDCR-approved charter. The roles and responsibilities of committee members and meeting procedures will be formally described in the charter.

The DSMC will provide its input to the National Institute of Dental and Craniofacial Research, Clinical Director and the PI.

The DSMC will be alerted if any of the following situations occur:

- An unexpected fatal or life-threatening event assessed as related to the use of study drug.
- Three or more participants with similar severe AEs (Grade 3 or 4) assessed as related to the use of study drug.

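### The planned primary safety summaries never report the toxicity that the endpoint defines (drug-related, Grade 3 or higher), and the only graded category leaves out serious events

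*Combined protocol and SAP*

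**What the plan says.** The primary endpoint is safety and tolerability. The synopsis (1.1.1) states: "Toxicity is defined as any study drug-related Grade 3 adverse event or higher". The table in Section 3 gives the same definition: "Toxicity is defined as any study drug-related Grade 3 or higher adverse event". Neither excludes serious events.

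Section 9.1 restates the primary endpoints as counts and rates of "serious adverse events, Grade 3 and 4 toxicities not fulfilling the criteria for SAE, and non-serious adverse events", together with disease flares. Section 9.3.2 lists, by treatment group and for the safety population, participants with "any AE, any related AE, any SAE, any Grade 3 and 4 toxicities not fulfilling the criteria for SAE", then non-serious adverse events and flares, with event totals for each category. Section 9.3.4 adds no category. It refers the reader to 9.2.2, which is the intent-to-treat population.

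The data are collected. Section 8.6.1 says: "All AEs will be graded for intensity (severity) according to CTCAE version 5.0 and relationship to study drug as described below". Section 8.7.4 lists, among the items captured for each event, the clinician's "assessment of severity, relationship to study product (assessed only by those with the training and authority to make a diagnosis").

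**The concern.** The trial exists mainly to study tolerability and toxicity (9.1.1), and its primary endpoint contains an explicit definition of toxicity, yet the list of primary summaries omits it. Relatedness appears only in a category without grade. Grade appears only in a category that excludes serious events and stops at Grade 4. Serious events are split by neither grade nor relatedness.

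Under 8.6.2, events that are fatal ("Results in death"), life-threatening or need hospitalization are serious. Related events of this kind are the gravest toxicities, and the graded row shuts them out by construction. A reader looking for the toxicity result may take that row for it.

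Two terms are also left open. Section 9.3.2 does not say whether the word toxicities carries the Section 3 meaning or covers events of any cause. Nor does the plan say which of the five causality categories in 8.7.2 count as drug-related for this endpoint. Section 7.2 sets the bar at possible relationship or above, but only for a withdrawal criterion.

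**Working it through.** The plan states no toxicity rate or powered sample size, so there is no figure to reproduce. The check is whether the listed categories determine the defined count.

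**Step 1: classify every type of event.** An event is related or not, Grade 3+ or not, serious or not, which gives 8 types. Two of them meet the Section 3 definition:

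| Event type | Rows of 9.3.2 in which it appears |
|---|---|
| Related, Grade 3+, non-serious | any AE, related AE, non-serious AE, Grade 3–4 non-SAE |
| Related, Grade 3+, serious | any AE, related AE, SAE |

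The second type falls in exactly the same rows as a related Grade 1–2 serious event, so the tables cannot tell the two apart. An unrelated Grade 3–4 non-serious event also falls in the graded row if toxicities means all-cause.

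**Step 2: bound the gap.** For one arm, let
- T = participants with at least one related Grade 3+ event (the Section 3 count),
- R = participants with a related Grade 3–4 non-serious event (the graded row, read as drug-related),
- S = participants with at least one serious event.

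T − R counts participants whose only related Grade 3+ events are serious, so 0 ≤ T − R ≤ S. If the row is all-cause, the lower bound for T falls to 0 and the upper bound R + S is unchanged (T also cannot exceed the number with a related event).

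**Step 3: weight of one participant.** Section 4.1 plans 20 on Tofacitinib and 10 on placebo, with up to 11 replacements. If all 41 were dosed at 2:1, the arms would be about 27 and 14.
- Tofacitinib: 1/20 = 5.0%; 1/27 = 3.7%
- Placebo: 1/10 = 10.0%; 1/14 = 7.1%

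**Step 4: sensitivity.** The values of R and S below are assumptions, and the row is read as drug-related.

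| Arm | R | S = 0 | S = 1 | S = 2 |
|---|---|---|---|---|
| Tofacitinib, n=20 | 3 | T = 3 | 3–4 | 3–5 (15–25%) |
| Tofacitinib, n=20 | 0 | T = 0 | 0–1 | 0–2 |
| Placebo, n=10 | 1 | T = 1 | 1–2 | not run |

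Between arms, take rows of 3/20 and 1/10, with 2 and 1 participants having a serious event:
- difference shown by the rows: 15% − 10% = +5 points
- lowest possible difference in T: 3/20 − 2/10 = −5 points
- highest possible difference in T: 5/20 − 1/10 = +15 points

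The extremes need the unseen events to fall in opposite ways in the two arms. They are limits, not expectations.

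**Step 5: evidence on the likely size.** The documents give no serious-event rate for this population. In the SLE trial of the same dose over 8 weeks (2.3.1, Table 4), 0 of 43 events on Tofacitinib and 2 of 28 on placebo were severe. Those are events, not participants, and severity is not seriousness, but they are compatible with a gap of zero here.

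**The case against.** The strongest reply is that nothing serious goes unreported. Every serious event is in the SAE row by arm, and pairing that row with severe non-serious events avoids double counting. The graded row is labelled as excluding serious events, so a careful reader would not take it for all toxicity. Section 9.1 says the endpoints include these categories, which is not exclusive wording. Section 9.2.1 promises that all safety data will be listed and summarised, and 9.2.3 makes every participant evaluable for toxicity from the first dose. Section 10.7 alerts the DSMC to "Three or more participants with similar severe AEs (Grade 3 or 4) assessed as related to the use of study drug", with no exclusion of serious events, and separately to unexpected fatal or life-threatening related events. The analyses are descriptive, no decision rests on the row, and the numerical illustration uses assumed counts.

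Much of this stands. No data are lost, the count can be derived from about 30 participants' records, and the illustration shows what is possible, not what is likely. But 9.2.1 names no summary of related events by grade, 9.2.3 names no summary at all, and the DSMC alerts are triggers during the trial, not results by arm. Labelling the row correctly does not supply the missing one. Wording on possible relatedness elsewhere (7.2, and 8.8.4 for unanticipated problems) does not set a cut-off for this endpoint. In a descriptive trial the tables are the primary result, so they should show what the endpoint defines.

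**Conclusion.** The concern holds. As written, the primary summaries in 9.1 and 9.3.2 do not report the toxicity that the synopsis and Section 3 define, and it cannot be reconstructed from the listed rows under either reading of toxicities. Read as drug-related, the graded row can only understate the defined count, by 0 to S participants per arm. Read as all-cause, it can be too low or too high. Each participant affected is worth up to 5.0 points on Tofacitinib and 10.0 on placebo at the planned sizes.

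The mismatch in definitions rests on the text alone. The size depends on how many participants have serious events, which the documents do not give. With no serious events and the drug-related reading, the gap is zero. It should be fixed because it concerns the primary endpoint and the repair is nearly free, not because a large distortion has been shown.

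**What to change.** 1. In 9.1 and 9.3.2, add by arm the number and percentage of participants, and the number of events, with at least one treatment-emergent drug-related adverse event of CTCAE Grade 3 or higher, serious or not, Grade 5 included.
2. State before unblinding which 8.7.2 categories count as drug-related, for example definitely, probably and possibly related.
3. Say whether toxicities in the existing non-SAE row means drug-related or all-cause.
4. Keep the existing categories as supportive summaries.

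Exact confidence intervals for the new row are optional. As a clerical matter, 9.3.4 should refer to 9.3.2 instead of 9.2.2. Sections 9.3.5 and 9.3.6 show the same numbering shift, since the general approach they cite is in 9.3.1.

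The cost is protocol wording and one derived row per arm. No new data, participants or alpha are needed.

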9.3.3 Analysis of the Secondary Endpoint(s)

Secondary endpoints listed in Section 3.0 will be analyzed for the ITT population. Continuous endpoints (e.g. change from baseline (Day 1) to end of treatment (Day 168) will be compared between treatments using analysis of covariance (ANCOVA) model with baseline as a covariate if normality assumption holds. Otherwise, the nonparametric alternative will be adopted. For repeated measures, linear mixed models will be used. For multi-omics data, transcriptional pathway analysis, graphical data visualization (heat maps, cluster analysis), and differential gene expression analysis will be performed.

Secondary endpoints will be analyzed by comparisons between the treatment (all SS participants receiving Tofacitinib) and placebo groups once the last participant completes the 28 weeks (196 days) of study.

- Change in the ESSDAI score between baseline and Day 168 (end of treatment).
- Change in the Physician's Global Assessment (PGA) scores between baseline and study day 168 (end of treatment).

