To investigate the effects of Tofacitinib on systemic biomarkers of SS as measures of biological effects that can be used as outcome measures to power a larger Clinical Trial.	The biological effects of Tofacitinib in this research population are unknown. Assessing for changes in major biological markers of SS will improve the understanding and potential uses of Tofacitinib in this and other disease states.	Changes in serum cytokines, autoantibody levels (e.g., ANA-Hep2 substrate, SSA, SSB autoantibody titers), complement proteins C3 and C4, markers of systemic inflammation such as ESR and CRP between baseline and study day 168
Tertiary/Exploratory		
Identify transcriptional changes in affected tissues due to JAK-STAT inhibition.	Target tissue (MSG) transcriptional landscape changes from baseline to Day 168 with respect to treatment allocation.	Transcriptional alterations and pathway analysis using RNA sequencing (RNAseq) on MSG and/or peripheral blood mononuclear cells (PBMC) between baseline and study day 168. Transcriptional and tissue compositional changes using single cell (sc)RNAseq on available tissue collected between baseline and study day 168.
Assess target tissue histopathological and architectural changes as a correlative measure with functional improvement.	Target tissue (MSG) changes in immune infiltration histopathology from baseline to Day 168 with respect to treatment allocation.	Change in MSG biopsy histopathology including focus score, infiltrate area, acinar density, and fibrosis.
Identify changes in infiltrating immune cells and the correlation with other markers of effect.	Target tissue (MSG) changes in immune infiltration from baseline to Day 168 with respect to treatment allocation.	Immunophenotyping of immune cell infiltrates in minor salivary gland biopsies by immunohistochemistry. We will specifically focus on numbers and or density of CD+3, CD20+, CD8+, CD4+, CD25+, Foxp3+ regulatory subsets and Th17 cells.
Identify changes in infiltrating immune cells and the correlation with other markers of effect.	Target tissue (MSG) changes in immune infiltration from	When tissue is available, alteration in minor salivary gland immune cell

Abbreviated Title: Tofacitinib in Sjögren's syndrome

Version Date: 07/01/2024

OBJECTIVES	JUSTIFICATION FOR ENDPOINTS	ENDPOINTS
	baseline to Day 168 with respect to treatment allocation.	populations by flow cytometry with attention to CD3+, CD20+ NK, CD8+, CD4+, CD19+, CD25+, Foxp3+ regulatory subsets.

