6.3 MEASURES TO MINIMIZE BIAS: RANDOMIZATION AND BLINDING

Randomization will be done by the NIH Clinical Research Center Pharmacy in conjunction with the statistician associated with the study. This is a two-arm, double blind study.

The study will utilize the stratified block randomization method to ensure that the Tofacitinib and placebo groups are balanced with respect to the baseline disease activity level. Eligible

Abbreviated Title: Tofacitinib in Sjögren's syndrome

Version Date: 07/01/2024

subjects will be stratified according to the ESSDAI score (0-1 vs. 2-13). Within each stratum, subjects will be randomly assigned by use of computer-generated blocks of size 3 with a 2:1 ratio to Tofacitinib or control group. Thus, participants will be randomized to either Tofacitinib or placebo in a 2:1 ratio overall. Both participants and investigators will be blinded to treatment allocation. Unblinding for analysis will occur once all the collected study data has been entered and the database is locked. Participants and local treating physicians will be informed of treatment allocation by a letter sent by certified mail, at that time.

The blind will be held by the statistician and the NIH Clinical Center Research Pharmacy. In cases where breaking the blind is necessary to provide clinical care to the participant, as determined by the PI and medically responsible team member, [name], the PI will contact the NIH Clinical Center Research Pharmacy and provide the treatment allocation information to the treating physician. Such participant(s) would be withdrawn from the study and followed up as described in section 4.10 above.

The Data and Safety Monitoring Committee (DSMC) may also request unblinding of treatment allocation or group assignment. These requests will be transmitted to the NIH Clinical Center Research Pharmacy by the PI. Data will be provided directly to the DSMC Chair without unblinding the investigators before the DSMC determines a plan of action.

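### Low severity: the ANCOVA in 9.3.3 names no term for the ESSDAI randomisation stratum; adding it for endpoints other than ESSDAI costs almost nothing and removes possible conservatism

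*Combined protocol and SAP*

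**What the plan says.** Section 6.3 uses stratified permuted blocks of three at 2:1. It says that "subjects will be stratified according to the ESSDAI score (0-1 vs. 2-13", so that the groups are "balanced with respect to the baseline disease activity level".

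Section 9.3.3 has continuous secondary endpoints "compared between treatments using analysis of covariance (ANCOVA) model with baseline as a covariate if normality assumption holds". If normality fails, "Otherwise, the nonparametric alternative will be adopted". Repeated measures go to linear mixed models. Section 9.1 also plans a repeated-measures analysis of change for ESSDAI, PGA, tear production and salivary flow. Neither place lists covariates for the mixed models.

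The endpoints affected are those other than ESSDAI:
- PGA, from the change in "Global Assessment (PGA) scores between baseline and study day 168 (end of treatment" listed in 9.3.3;
- "Change in salivary flow rates between baseline and study day 168" (Section 3);
- the biomarkers (Section 3), beginning "Changes in serum cytokines, autoantibody levels".

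Section 9.3.1 commits to two-sided 5% tests and 95% confidence intervals for efficacy variables, although 9.1 describes every analysis as descriptive and exploratory.

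**The concern.** Stratified blocks hold the 2:1 ratio nearly constant within each stratum, so differences between strata largely drop out of the true sampling variance of the treatment effect. A model without the stratum leaves those differences in its residual variance. If they matter for the outcome, the reported standard error is too large, the test rejects too rarely and the interval is too wide.

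For ESSDAI, the baseline covariate is the stratifying score or close to it, so little is lost. For PGA, salivary flow and biomarkers, the endpoint's own baseline may not carry what the ESSDAI split carries.

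The stakes are modest. Section 3 wants the biomarker effects as outcome measures for powering a larger trial, and about 30 participants with 10 on placebo leave little precision to give away.

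**Working it through.** **Inputs from the documents.** Two strata, blocks of three, 2:1 (6.3); 20 tofacitinib and 10 placebo (4.1); withdrawal of about 25% and up to 30 + 11 = 41 enrolled (7.2); ANCOVA on own baseline (9.3.3); two-sided 5% and 95% (9.3.1). The plan gives no power figure to reproduce, and 9.1.1 calls the sample size arbitrary. The withdrawal allowance is about right (30/0.75 = 40, against 41 stated). It matters here only because it puts the number analysed anywhere from about 23 (30 × 0.75 = 22.5) upwards.

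**Assumed inputs.** The split between strata, the correlation of outcome with own baseline, the association of stratum with that baseline, and the residual stratum shift.

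**Step 1: direction and rough size.** Let σ be the residual SD, δ the stratum shift given baseline, p the share in one stratum and r the stratum-baseline correlation. Without the stratum the residual variance is about σ² + δ²p(1−p)(1−r²); with it, σ². The ratio of interval widths, with to without, is about 1/√(1 + (δ/σ)²p(1−p)(1−r²)). With p = 0.5 and r = 0.3, p(1−p)(1−r²) = 0.25 × 0.91 = 0.2275, so:
- δ = 0.25σ: 1/√1.0142 = 0.993, or 0.7% narrower;
- δ = 0.5σ: 1/√1.0569 = 0.973, or 2.7% narrower;
- δ = 1.0σ: 1/√1.2275 = 0.903, or 9.7% narrower.

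These are before the cost of the extra term.

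**Step 2: the degree of freedom.** With 30 analysed, residual df go from 27 to 26 and t from 2.052 to 2.056 (+0.18%). With 23, t goes from 2.086 to 2.093 (+0.34%). With 41, the rise is 0.09%. Any chance association of treatment with stratum among those analysed adds to this, and it grows when participants are lost.

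**Step 3: simulation of the planned design.** Two sets were run; entries are the change in 95% interval width on adding the stratum.
- Set A: 10,000 trials per cell; strata 15/15 to 3/27; outcome-baseline correlation 0.3-0.6; strata 0 or 1 SD apart on baseline; shift in within-stratum outcome SD.
- Set B: 5,000 trials per cell; share in one stratum 0.2, 0.5 or 0.8; r = 0.3, with 0.6 as a check at 30 analysed; shift in residual SD.

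| Shift | A, 30 analysed | A, type I error without stratum | B, 30 analysed | B, 25% of 30 lost | B, 25% of 41 lost |
|---|---|---|---|---|---|
| 0 | +0.2 to +0.6% | not listed | +0.4 to +1.0% | +1.6% | +0.9% |
| 0.25 | 0 to −1.1% | 4.4-5.3% | not run | not run | not run |
| 0.5 | −0.8 to −4.6% | 3.9-4.9% | −1.2 to −2.4% | −0.3 to −1.2% | −1.0 to −2.1% |
| 1.0 | −4.2 to −15.8% | 2.3-4.2% | −6.2 to −9.6% | −5.1 to −8.9% | −5.8 to −9.2% |

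At 1.0 SD and r = 0.3 in set B, coverage was 95.7-96.6% without the stratum and 94.6-95.4% with it. Power at a 0.8 SD effect rose by about 4 to 8 points (0.419 to 0.493 with 30 analysed and equal strata on average). A further run at outcome-baseline correlation 0.5 with 7 of 30 lost put the effect at a 0.25 SD shift between 0.7% wider and 0.1% narrower.

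The 15.8% in set A needs equal strata and correlation 0.6, where a shift of 1.0 outcome SD equals 1/√(1 − 0.36) = 1.25 residual SD.

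**Step 4: where the term does not help.**
- *Sparse strata.* With a 1/29 split it widens the interval by 1.9% at no shift and still by 1.2-1.5% at 0.5 SD. With 2/28 it costs 1.0-1.1% at no shift and changes width by at most 0.2% either way at 0.5 SD.
- *ESSDAI itself.* Under assumed score distributions the stratum correlates 0.61-0.78 with the score, and adding it widened the interval by 1.1-1.2% with no useful change in coverage.

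**The case against.** The strongest reply is that the problem is conditional. Baseline PGA rates global disease activity (8.2.6) and may already hold much of what an ESSDAI split holds. At 0.5 SD or less the conservatism is hard to see, and with the expected withdrawals the benefit at 0.25 SD disappears. All of this stands, and it keeps the point optional.

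It is also fair that 9.3.3 does not say baseline is the only covariate. The text names one covariate and is silent on the stratum. For the mixed models, which list no covariates, this is missing detail and not a decision to exclude.

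A reader might infer more than the documents support:
- *A biased estimate or too many false positives.* Randomisation protects the estimate, and the error, if any, is towards too few rejections.
- *Poor planning values for the later trial.* In set A the actual SD of the treatment estimate differed by under 1% at shifts up to 0.5 SD and by at most about 3% at 1.0 SD. The reported standard error is what is off.
- *A defect in the primary analysis.* Section 9.3.2 summarises safety by counts and percentages, which no covariate touches.
- *That the unnamed nonparametric fallback belongs to this point.* It is a separate matter. In a skewed-outcome check with no stratum effect, rank ANCOVA on baseline had 61-64% power against 50-56% for a Wilcoxon test on change. That gap comes from dropping baseline, not the stratum.

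**Conclusion.** The point holds as a low-severity, near-free improvement. The plan randomises within ESSDAI strata and names no stratum term in any efficacy model. For endpoints other than ESSDAI, the tests and intervals are conservative if the stratum is prognostic beyond own baseline, which the documents neither show nor rule out.

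A large gain requires a shift near 1.0 SD, and the top of that range also requires equal strata and a high baseline correlation. The downside of adding an uninformative stratum is 1.6% in interval width at most in the cases run, with the sparse-stratum rule in place. The balance favours adding the term, but a team that leaves it out loses some precision at worst, not validity.

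**What to change.** Add to 9.3.3, and refer to it from the repeated-measures analysis in 9.1:

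*For endpoints other than ESSDAI, the ANCOVA and linear mixed models will include treatment, the endpoint's Day 1 baseline and the ESSDAI stratum (0-1 or 2-13) as used at randomisation. The stratum term will be dropped for an endpoint if either stratum has fewer than 3 participants with data, or has participants from one arm only.*

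The threshold of 3 is one full block and follows from the sparse-stratum results. Because Section 6.3 does not say which visit's ESSDAI sets the stratum, the analysis should use the stratum recorded at assignment and not rederive it. The wording should be settled before unblinding, given that "The blind will be held by the statistician and the NIH Clinical Center Research Pharmacy".

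The cost is a text change and one degree of freedom. It needs no new data and no change to sample size or conduct.
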